5.1.2 Subsequent Cycles

Patients can receive treatment if they do not meet dose delay/dose modification criteria (see section 6). All toxicities must have resolved to grade 1 or less, or the patient's baseline, prior to initiating subsequent cycles.

5.2 Treatment Regimen Phase 1

Cycle = 28 days

|--|

Phase I/Ib Study of TGR-1202 plus Ibrutinib in Patients with Select B-Cell Malignancies

Version Date: 10.23.2019

			CLL		
1 400 mg		560 mg	420 mg		
2 600 mg		560 mg	420 mg		
3 800 mg		560 mg	420 mg		
If ≥ 2 DLT's in either Cohort 1, 3- 6 pts will enroll in Cohort -1 as follows:					
-1	200 mg	560 mg	420 mg		
If ≥ 2 DLT's in a Cohort -1 treatment group, study will be terminated					

Dose level 1 will be the starting level for patients in both the CLL and MCL arms. Patients will continue daily administration of TGR-1202 + ibrutinib until progression or removal from study per investigator decision.

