5.6.3 Dose-Limiting Toxicity- Cycle 1 for Phase 1 Only

Toxicity will be assessed utilizing the National Cancer Institute Common Terminology Criteria for Adverse Events (NCI CTCAE) v4.0 (http://evs.nci.nih.gov/ftp1/CTCAE/CTCAE) with the exceptions recommended by the IWCLL guidelines for the diagnosis and treatment of CLL defined in Appendix D.

Toxicity will be considered dose-limiting if it occurs during the first cycle (28 days) of treatment with TGR-1202 and ibrutinib, and is considered at least possibly related to either TGR-1202 and/or ibrutinib. Any event defined below, unless the investigator considers the event clearly unrelated to study drug or due to extraneous causes, will be considered a dose-limiting toxicity.

Dose-limiting toxicities will be defined as the following:

- Grade 4 anemia; Grade 4 neutropenia lasting >7 days (while receiving growth factor support); Grade 4 thrombocytopenia lasting > 7 days; Grade ≥3 febrile neutropenia; and Grade ≥3 thrombocytopenia with Grade >2 hemorrhage;
 - For patients with CLL/SLL, hematologic toxicity will be graded according to the IWCLL guidelines (Appendix D) and Grade 4 toxicity lasting >7 days will be considered dose limiting; this will not apply to CLL/SLL patients who are not evaluable for hematologic toxicity by IWCLL criteria (see Appendix D)
- Grade ≥ 3 non-hematologic toxicity unresponsive to standard supportive care measure with the exception of:
 - o Asymptomatic Grade ≥3 lab abnormalities that resolve to ≤ Grade 1 or baseline within 7 days;
- Treatment delay of ≥ 14 days due to unresolved toxicity; and
- Non-hematologic toxicity of Grade 2 (at any time during treatment) that, in the judgment of the Investigators, Study Chair, and the Medical Monitor, is dose-limiting.

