Adverse events meeting the above definitions but are clearly unrelated to study drug will not be considered DLTs. In rare instances an event may fall within the definition of a DLT as defined above but the event may not be considered a DLT (i.e., not clinically meaningful/significant). If this occurs, a discussion between the Principal Investigator, Investigator(s), a TG Therapeutics representative, will take place to thoroughly review the event and supporting data, and the reasons for not considering the event a DLT will be clearly documented with supporting rationale. In addition, other events may occur which do not meet the definition of a DLT but are concerning to the Principal Investigator, other Investigator(s) and/or the TG Therapeutics representative, and may be then considered to be DLTs.

5.6.4 Determination of Dosing-Limiting Toxicity- Cycle 1

The patient population used for determination of DLT will consist of patients who have met the minimum safety evaluation requirements of the study, and/or who have experienced a DLT. Minimum safety requirements will be met if, during Cycle 1 of treatment in the Phase I part of the study, the patient receives at least 80% of planned ibrutinib and TGR-1202 doses, completes the required safety evaluations, and is observed for at least 28 days following the first dose of TGR-1202 and ibrutinib. Patients who experience a DLT will be considered evaluable regardless of the number of doses received.

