5.7 General Concomitant Medication and Supportive Care Guidelines

The following treatments are prohibited while on clinical trial: other investigational drug treatments or study participation, radiation therapy (except as described above), hormonal therapy for cancer, cancer immunotherapy or other biologic therapy. Low dose glucocorticoids (≤ 20 mg per day of prednisone or equivalent) may be administered for premedication or AE management after discussion with the Principal Investigator.

Neutropenia: Granulocyte colony stimulating factor (G-CSF; filgrastim, pegfilgrastim or other acceptable G-CSF) may be used during the course of the study at the discretion of the investigator. The drug(s) should be used at a dose/schedule specified in the package insert.

Antiemetics: Both TGR-1202 and ibrutinib are considered to be of low emetogenic potential, and therefore no anti-emetics are required by protocol, but may be used as needed at the investigators' discretion.

Tumor Lysis Syndrome: In subjects at risk for tumor lysis syndrome in the opinion of the treating investigator, prophylaxis with allopurinol or institutional standards should be considered.

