6. DOSING DELAYS/DOSE MODIFICATIONS

Patients should be assessed clinically for toxicity at each visit using the NCI CTCAE v4.0 (http://evs.nci.nih.gov/ftp1/CTCAE/CTCAE) grading scale. Hematologic toxicity for CLL patients will be assessed by the IWCLL defined in Appendix D.

Dosing will occur only if a patient's clinical assessment and laboratory test values are acceptable.

It should be noted that both TGR-1202 and ibrutinib are generally well-tolerated oral agents with favorable adverse event profiles. Therefore, where possible, investigators will be encouraged to

continue patients on the full dose of both drugs. The dose reduction criteria on this study are intentionally lenient to allow investigators to continue patients on full dose given the likelihood that many adverse events will be related to underlying disease and co-morbidities.

Dose modification and or intervention with supportive care recommendations for TGR-1202 (for ibrutinib follow prescribing information) are provided below, however, final discretion lies with the treating investigator in regard to more or less aggressive intervention. Decisions about which specific investigational agent (or if both agents) needs to be reduced, and actual dose reductions, as well as the number of dose reductions will be made after discussion between the treating investigator and the Principal Investigator

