6.2.1 Hematologic Toxicity

Table 1 Dose Modifications for Hematologic Toxicity (For patients with CLL, Appendix D IWCLL Grading Scale should be referenced).

Worst CTCAE Grade Toxicity	Recommended Action to be Taken
	HEMATOLOGIC
Neutropenia (ANC)	
Grade 1	Maintain dose level
Grade 2	First incidence: Maintain dose level Second incidence: Consider growth factor support

Grade 3 / 4	Hold dose until resolved to ≤ Grade 2 or baseline, consider
1st Occurrence	growth factor support.
Grade 3 / 4	Hold dose until resolved to ≤ Grade 2 or baseline, consider
Subsequent Occurrences	growth factor support. Consider reducing dose as per Table 3 if
_	warranted.
Thrombocytopenia	
Grades 1,2, and 3 with no	Maintain dose level
evidence of bleeding	
Grade ≥3 thrombocytopenia	Hold dose until to \leq Grade 2 or baseline and bleeding resolves,
with Grade >2 bleeding	consider platelet transfusion as necessary.
Grade 4	Hold dose until to \leq Grade 2 or baseline, consider platelet
1st Occurrence	transfusion as necessary.
Grade 4	Hold dose until to ≤ Grade 2 or baseline, consider platelet
Subsequent Occurrences	transfusion as necessary. Consider reducing dose as per Table 3
_	if warranted.

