APPENDIX D IWCLL GRADING SCALE FOR HEMATOLOGIC TOXICITY IN CLL STUDIES

Grade	Decrease in Platelets [¢] or Hb [‡] (nadir) from Pretreatment Value, %	Absolute neutrophil count/μL (nadir)§
0	No change to 10%	≥2000
1	11% - 24%	≥1500 and <2000
2	25% - 49%	≥1000 and <1500
3	50% - 74%	\geq 500 and <1000
4	≥75%	< 500

Grades: 1, mild; 2, moderate; 3 severe; 4 life-threatening; 5 fatal. Death occurring as a result of toxicity at any level of decrease from pretreatment will be recorded as grade 5.

 ϕ Platelet decrease, must be below normal levels for grades 1 to 4 at any level of decrease, the platelet count is <20X 10⁹/L (20,000/μL), this will be considered grade 4 toxicity, unless a severe or life-threatening decrease in the initial platelet count (eg, 20 X 10⁹/L [20 000/μL]) was present pretreatment, in which case the patient is not evaluable for toxicity referable to platelet counts.

‡ Hb levels must be below normal levels for grades 1 to 4. Baseline and subsequent Hb determinations must be performed before any given transfusions. The use of erythropoietin is irrelevant for the grading of toxicity but should be documented.

§ If the absolute neutrophil count (ANC) reaches $<1 \times 10^9/L$ ($1000/\mu L$), it should be judged to be grade 3 toxicity. Other decreases in the white blood cell count, or in circulating neutrophils, are not to be considered because a decrease in the white blood cell count is a desired therapeutic endpoint. A gradual decrease in granulocytes is not a reliable index in CLL for stepwise grading of toxicity. If the ANC was $<1 \times 10^9/L$ ($1000/\mu L$) before therapy, the patient is not evaluable for toxicity referable to the ANC. The use of growth factors such as G-CSF is not relevant to the grading of toxicity, but should be documented.

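### In the MCL arm, afebrile Grade 4 neutropenia lasting more than 7 days meets no listed DLT criterion if no G-CSF is given and the delay stays under 14 days

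*Combined protocol and SAP*

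**What the plan says.** The general hematologic bullet of Section 5.6.3, which governs MCL, includes "Grade 4 neutropenia lasting >7 days (while receiving growth factor support". For CLL/SLL a sub-bullet applies instead: "Grade 4 toxicity lasting >7 days will be considered dose limiting". It has no growth-factor condition, and Appendix D, the CLL grading scale, states: "The use of growth factors such as G-CSF is not relevant to the grading of toxicity, but should be documented".

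G-CSF is optional. Under Section 5.7 it "may be used during the course of the study at the discretion of the investigator". For Grade 3/4 neutropenia, Table 1 (Section 6.2.1) advises "Hold dose until resolved to ≤ Grade 2 or baseline, consider" growth factor support. Section 6 makes Table 1 a recommendation: "final discretion lies with the treating investigator". Before a further cycle, Section 5.1.2 requires: "All toxicities must have resolved to grade 1 or less", or a return to baseline.

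Section 5.6.4 admits a patient without a DLT to the DLT population only if "the patient receives at least 80% of planned ibrutinib and TGR-1202 doses". A patient with a DLT is evaluable whatever doses were taken. Section 5.6.5 provides replacement for patients who withdraw from treatment in Cycle 1.

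Two judgement routes exist. The end of Section 5.6.3 lets the investigators or the company representative treat other worrying events as DLTs. Sections 5.2.2 and 5.2.4 provide a safety review before each escalation.

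**The concern.** The MTD in each disease group is the primary endpoint (Section 13), and cohorts hold 3 to 6 patients, so one event can change a decision. As written, two MCL patients with the same neutropenia can be scored differently because one physician gave G-CSF and the other did not. Reading the parenthesis as meaning despite support does not remove the difficulty, since G-CSF must still have been given.

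The dose rule adds to the problem. A hold prompted by the toxicity can itself make the patient non-evaluable, so a serious event may drop out of the data that set the MTD.

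**Working it through.** **1. Listed criteria in Section 5.6.3, for an afebrile MCL patient with Grade 4 neutropenia for more than 7 days, no G-CSF and a delay under 14 days**

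- Neutropenia item: not met, because no growth factor was given.
- Anemia and thrombocytopenia items: different events.
- Febrile neutropenia: not met, because the patient has no fever.
- Grade 3 or higher toxicity, and Grade 2 toxicity by judgement: both limited to non-hematologic events.
- Treatment delay: not met, because it needs 14 days or more.
- Grade 4 hematologic toxicity for more than 7 days without a G-CSF condition: CLL/SLL only.

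No listed item applies.

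**2. The 80% rule**

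0.80 x 28 = 22.4, so at least 23 doses of each drug are needed and at most 5 may be missed.

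- 5 missed: 23/28 = 82.1%, passes.
- 6 missed: 22/28 = 78.6%, fails.
- 8-day hold within Cycle 1: 20/28 = 71.4%, fails.
- 13-day hold within Cycle 1: 15/28 = 53.6%, fails.

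A patient held under Table 1 for 6 or more Cycle 1 doses therefore leaves the DLT population. If that patient stays on study, Section 5.6.5 gives no replacement rule. A patient whose dosing continues is an evaluable non-DLT. A hold that starts on Day 24 or later also passes the dose rule, but that event runs past Cycle 1 and the point does not depend on it.

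**3. How often the 14-day criterion catches the event**

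Sections 5.4.3 to 5.4.6 schedule counts on Days 8, 15 and 22 and on Cycle 2 Day 1, each within 3 days. Suppose Grade 4 is found on Day 8 and is still present on Day 15. That shows 7 days, not more than 7. The next nominal count is Day 22, and 22 - 8 = 14 days of hold, which is a listed DLT. Onset on Day 15 gives the same result at Cycle 2 Day 1 (29 - 15 = 14). This assumes that a hold within a cycle counts as treatment delay. Escape needs extra or shifted counts, a departure from Table 1, or late onset.

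**4. Size**

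The 3+3 rule gives P(escalate) = (1-p)^3 + 3p(1-p)^5. At p = 10% to 60% this is 0.906, 0.709, 0.494, 0.309, 0.172 and 0.082, which reproduces Table 5.

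Let o be the rate of other DLTs, q the rate of the neutropenia described above whether or not G-CSF is given, and g the share given G-CSF. Rates are taken as additive, and neither judgement route is used.

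- All counted: p = o + q.
- Untreated patients kept as non-DLTs: p = o + qg.
- Untreated patients excluded and slots refilled: p = (o + qg)/(1 - q(1-g)).

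For o = 0.20, q = 0.02, g = 0.5, p is 0.220, 0.210 and 0.210/0.990 = 0.212. All inputs are assumptions. With o = 0.20:

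| q, g | All counted | Excluded, refilled | Kept as non-DLT | Rise |
|---|---|---|---|---|
| 1%, half | 0.687 | 0.696 | 0.698 | about 0.01 |
| 2%, half | 0.665 | 0.682 | 0.687 | about 0.02 |
| 5%, half | 0.600 | 0.642 | 0.654 | 0.04-0.05 |
| 10%, none | 0.494 | 0.660 | 0.709 | 0.17-0.21 |

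With o at 10% or 30%, the 2%/half case gives a rise of 0.01-0.02 and the 10%/none case 0.12-0.20.

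**The case against.** The strongest reply is that this is a recognisable design choice with safeguards around it. Ibrutinib alone gives 29% Grade 3 or 4 neutrophil decrease in MCL (Section 7.1.2), so it is reasonable to reserve the DLT label for neutropenia that persists despite G-CSF. Weekly counts with the hold followed send many untreated events to the 14-day criterion. Worrying events can be upgraded, every cohort is reviewed, at least six patients are needed at the MTD, and 12 more are treated in Phase Ib.

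Much of this stands as a limit on size. It does not close the gap. The text requires that G-CSF was given and says nothing about patients who did not receive it. The upgrade clause is optional and sets no threshold, and the Phase Ib patients are treated after the dose has been chosen.

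A reader might infer that recorded toxicity can only be understated and that this always favours escalation. That does not follow for excluded patients. Section 5.6.5 replaces only those who withdraw, so a held patient leaves the cohort one evaluable patient short, and the text does not say that escalation then proceeds. The excluded column above needs the added assumption that slots are refilled.

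A reader might also infer that the CLL/SLL rule can simply be copied. Appendix D makes patients with a pretreatment ANC below 1000/µL not evaluable for neutrophil toxicity, and MCL has no such exemption although Section 3.1.4 admits an ANC of 500. If Grade 4 means below 500 (a cut shown here only in Appendix D), a patient entering just above that level could become a DLT after a trivial fall.

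**Conclusion.** The gap in the listed criteria is real but narrow: MCL, afebrile, more than 7 days at Grade 4, no G-CSF, total delay under 14 days. Such an event reaches the primary endpoint only by discretion. When the hold costs 6 or more Cycle 1 doses, the toxicity itself removes the patient from the DLT population.

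The size is unknown and probably small. The documents give neither the event rate nor the rate of G-CSF use. The 29% figure pools Grades 3 and 4 of any duration and is not limited to Cycle 1. At 1-2% with half given G-CSF, the rise of about 0.01-0.02 is small beside the steps of 0.09-0.22 between adjacent rows of Table 5. It goes to zero as the event becomes rare or G-CSF becomes universal. A reader might take the 0.17-0.21 row as the expected effect, but it needs a 10% event rate and no G-CSF use, and the documents support neither. The point is worth fixing because it bears on safety and the MTD and the change is cheap.

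**What to change.** In Section 5.6.3, for MCL, replace the growth-factor parenthesis with *regardless of growth factor use*, and record G-CSF use. Add a baseline rule matching Appendix D: patients with a pretreatment ANC below 1000/µL are either not evaluable for neutrophil-count DLTs or are judged case by case under the discretionary provisions of Section 5.6.3. Patients who meet the revised criterion are then evaluable under Section 5.6.4 whatever doses they received. Management of neutropenia need not change.

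If MCL escalation is already complete, tabulate Cycle 1 Grade 4 neutropenia lasting more than 7 days by G-CSF use and baseline ANC, include patients excluded under the 80% rule, and confirm that the MTD holds.

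The cost is a short amendment or one table, with no added procedures. The downside is that a few more MCL events may count as DLTs and could hold the MTD at a lower level. The attribution rule and the documented review of events judged not clinically meaningful, both in Section 5.6.3, still apply.

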5.6.5 Replacement of Patients

Patients who discontinue treatment early due to disease progression or withdrawal will be asked to have all end-of-treatment safety evaluations performed as described in the protocol. If a patient withdraws from treatment during Cycle 1 due to any reason other than DLT and does not meet the minimum requirements for inclusion in the DLT-determining population described above, that patient will be replaced.

5.7 General Concomitant Medication and Supportive Care Guidelines

The following treatments are prohibited while on clinical trial: other investigational drug treatments or study participation, radiation therapy (except as described above), hormonal therapy for cancer, cancer immunotherapy or other biologic therapy. Low dose glucocorticoids (≤ 20 mg per day of prednisone or equivalent) may be administered for premedication or AE management after discussion with the Principal Investigator.

Neutropenia: Granulocyte colony stimulating factor (G-CSF; filgrastim, pegfilgrastim or other acceptable G-CSF) may be used during the course of the study at the discretion of the investigator. The drug(s) should be used at a dose/schedule specified in the package insert.

Antiemetics: Both TGR-1202 and ibrutinib are considered to be of low emetogenic potential, and therefore no anti-emetics are required by protocol, but may be used as needed at the investigators' discretion.

Tumor Lysis Syndrome: In subjects at risk for tumor lysis syndrome in the opinion of the treating investigator, prophylaxis with allopurinol or institutional standards should be considered.

5.8 Criteria for Taking a Participant Off Protocol Therapy

Duration of therapy will depend on individual response, evidence of disease progression and tolerance. If a participant is found by the treating investigator and by the overall PI to show clinical benefit from study treatment, the patient may remain on treatment. In the absence of treatment delays due to adverse event(s), treatment may continue until one of the following criteria applies:

Patients will be discontinued from trial treatment for any of the following reasons:

Phase I/Ib Study of TGR-1202 plus Ibrutinib in Patients with Select B-Cell Malignancies

Version Date: 10.23.2019

- Disease progression
- Irreversible or intolerable toxicity or abnormal laboratory values thought to be related to drug toxicity
- Patient requests to withdraw consent or discontinue treatment
- Pregnancy
- Inability of the patient to comply with trial requirements
- Conditions requiring therapeutic intervention not permitted by the protocol
- Inter-current illness (this will be at the investigator's discretion)
- Non-compliance/lost to follow-up
- Discontinuation of the study by the Sponsor

After withdrawal from protocol treatment, patients must be followed for AEs for 30 calendar days after their last dose of either trial drug. All new AEs occurring during this period must be reported and followed until resolution, unless, in the opinion of the investigator, these values are not likely to improve because of the underlying disease. In this case the investigators must record his or her reasoning for this decision in the patients' medical records and as a comment on the Case Report Form (CRF).

All patients who have CTCAE grade 3 or 4 laboratory abnormalities at the time of withdrawal should be followed until the laboratory values have returned to grade 1 or 2, unless it is, in the opinion of the investigator, not likely that these values are to improve because of the underlying disease. In this case, the investigator must record his or her reasoning for making this decision in the patients' medical records and as a comment on the CRF.

A QACT Treatment Ended/Off Study Form will be filled out when a participant is removed from protocol therapy. This form can be found on the QACT website or obtained from the QACT registration staff. External sites should submit the form to the Research Project Manager.

In the event of unusual or life-threatening complications, treating investigators must immediately notify the Overall PI, [name] at [contact], or page through [contact].

5.8.1 Pregnancy

During the course of the trial, all female patients of childbearing potential (the definitions of "women of childbearing potential" are listed in Appendix C) must contact the treating investigator immediately if they suspect that they may be pregnant (a missed or late menstrual period should be reported to the treating investigator).

If an investigator suspects that a patient may be pregnant prior to administration of trial drug(s), the trial drug(s) must be withheld until the result of the pregnancy test is confirmed. If a pregnancy is confirmed, the patient must not receive any trial drug(s), and must be discontinued from the trial.

If an investigator suspects that a patient may be pregnant after the patient has been receiving trial drug(s), the trial drug(s) must immediately be withheld until the result of the pregnancy test is confirmed. If a pregnancy is confirmed, the trial drug(s) must be immediately and permanently stopped, the patient must be discontinued from the trial, and the investigator must notify the Overall PI as soon as possible. If a patient becomes pregnant while enrolled in the trial, an SAE

form should be completed and faxed to the Overall PI expeditiously. For more details regarding handling and reporting of pregnancies that occur during treatment, see Appendix C.

5.9 **Duration of Follow Up**

Participants will be followed for survival after discontinuing protocol therapy every 3 months for up to 2 years or until the patient receives their next CLL/MCL-directed therapy or until death, whichever occurs first. Participants removed from protocol therapy for unacceptable adverse event(s) will be followed until resolution or stabilization of the adverse event.

For patients continuing to follow up at the treating institution, regular visits should occur every 3 months and efficacy assessments should occur at the investigator's discretion. For patients no longer treated at the original institution, phone contact should occur every 3 months with documentation of disease status or date of death obtained whenever possible. Patients should be followed for survival every three months for up to two years or until death, or next CLL/MCL directed therapy.

